## **4.2 Blinding**

Only the patients will be blinded to the treatment(s) received.

## **4.3 Study Assessments**

VAS Scale (comfort and pain), at 3:45 and 18:45 of each treatment session

Preference Questionnaire, at 18:45 of each treatment session

PHQ-9 Depression Scale, at 18:45 of each treatment session

## **5 Sample Size Determination**

A sample size of 40 total subjects, twenty to begin treatment with each of the two study arms, was selected as sufficient to perform a preliminary assessment of the differences between the two repetitive transcranial magnetic stimulation (rTMS) therapies for MDD. The sample size is not based on formal power requirements for a statistical hypothesis test but is based on a desire to obtain a reasonable initial data set for exploratory and planning purposes.

## **6 Statistical Analyses**

Statistical Analysis Plan		Page 8 of 18
Sponsor Neuronetics	Study Comfort Start	Version 1.0

## **6.1 General Considerations**

Statistical analyses will be performed by the Biostatistics Section of the Sponsor or its designee. Any additional or supplemental data analyses performed independently by the Investigator should be submitted to the Sponsor for review and approval.

Except where otherwise specified, the following general principles apply to the planned statistical analyses. It is intended that all statistical analysis will be conducted using the EasyMedStat package within the sponsor database. If necessary, some summary analyses may be generated by a sponsor designee utilizing SAS version 9.4 or later, or other widely-accepted statistical or graphical software as required.

### **6.1.1 Descriptive Statistics**

Continuous data will be summarized with mean, standard deviation, median, minimum, maximum, and number of evaluable observations. Categorical variables will be summarized with frequency counts and percentages. Confidence intervals may be presented, where appropriate.

### **6.1.2 Study Day**

Study day 1 is the date of the first day of the Dose Ramp Phase. Day in study will be calculated relative to that day as follows:

Study Day = Procedure/Assessment Date – Date of first day of the Dose Ramp Phase + 1

For each subject, duration in study will be based on last study contact date which is the latest date of all follow-up visits, assessments, adverse event onset or resolution, and study exit including date of death.

Duration variables will be calculated as follows:

Duration Days = Start Date – End Date

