Next, the PHQ-9 questionnaire will be completed, and subjects will have their Motor Threshold determined by the standard of care practice of the treating clinician and be randomized to receive their first rTMS stimulation with either treatment X or treatment Y.

The %MT treatment goal of 120% will be established by the physician. Subjects will have their Motor Threshold determined by the standard of care practice of the treating clinician and the first stimulation will be programmed to begin at 90% MT. Subjects will then be randomized to rTMS stimulation with either treatment X or treatment Y and have their first randomized stimulation treatment with the NeuroStar TMS Therapy System. Subject MT may be re-established and documented at the discretion of the treating physician at any time.

Treatment Assessments: Once TMS therapy begins, adjustments to lower the stimulation intensity can begin immediately, as needed, for subject tolerance. Every 3:45 minutes the TMS treater will assess if the subject can tolerate escalating the treatment MT by 10%. At each interval and the end of treatment, the treater will record the current %MT achieved. The goal will be to reach and sustain the target MT established by the treating physician of 120%MT. Once the target MT has been achieved and sustained for 3:45 minutes, recording and increases of %MT may be discontinued, but re-started at 3:45 minute intervals if %MT is subsequently reduced.

At minute 3:45, and at the end of the treatment session, the subject will be asked to complete a Visual Analog Scale (VAS), for Comfort/Pain.

If the subject reaches the prescribed %MT at Treatment Visit 1, the next study visit will be the start of the crossover phase of the study (Crossover Treatment 1), if not, they will continue to the next visit of the Ramp Phase.

Treatment Visits 2-5

Subjects will start treatment at the %MT established in the previous session and all study treatment procedures completed on Treatment Visit 1 will be repeated and documented for Treatment Visits 2-5. In addition, at the first time interval of 3:45, subjects will be asked a preference question - if they prefer the current treatment, last treatment, or if they cannot determine a difference. This question will be repeated at the end of the treatment visit.

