## **4 Study Design**

This is a prospective, randomized, single center, single blind study conducted in an adult population being treated for MDD (major depressive disorder).

For each patient, the study will consist of up to approximately 14 days, one hour for screening and 30 minutes during each daily treatment session. The goal of the study is to monitor and compare patient comfort (treatment area sensitivity) using two different treatment protocols at the start of TMS therapy where the stimulation intensity is typically escalated over 1-10 treatments until the patient is comfortable with the prescribed treatment dose (% MT; typically, 120%).

Each subject, of approximately 40, will be treated with rTMS for MDD as diagnosed and prescribed by their treating physician. Following consent and successful study qualification, study subjects will be randomized to the standard Dash protocol or the modified Dash protocol with the SoftStart feature enabled.

Prior to rTMS stimulation, the Motor Threshold (MT) will be established for each subject individually. Total treatment time per day is 18 minutes 45 seconds for either of the two treatments. Every treatment day patients will receive 75 fifteen second cycles. Each cycle is a 40 pulse train of 4 seconds with 11 seconds off (Dash), or a 50 pulse train of 5 seconds with 10 seconds off (Soft Start Dash). The extra 10 pulses per Soft Start Dash train are an eight pulse ramp-up sequence and a two pulse ramp-down sequence.

At the start of the 6th Treatment session or the session after the subject reaches the prescribed dose, the subject will be switched to the alternative treatment protocol and continue to alternate treatment each day for the next 4 treatments.

Each day of these 4 treatment sessions, at end of the first time interval (3:45 min, total of a set of 15 fifteen second cycles) and the end of the session, the subject will complete the comfort/pain questionnaire and be asked whether they preferred the current treatment, or the treatment received at the previous session (Today's Treatment, Last Treatment, No Difference).

Statistical Analysis Plan		Page 7 of 18
Sponsor Neuronetics	Study Comfort Start	Version 1.0

During treatments, the subject will be asked to complete several questionnaires, including comfort/pain, treatment preference, and depression questionnaires.

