### **6.6.3 Secondary Endpoints**

The secondary endpoints may be assessed via superiority or non-inferiority testing, with any non-inferiority margins to be defined, or may be assessed with descriptive summaries only.

The Secondary study outcomes will be determined as follows:

The ability to reach the prescribed treatment intensity, the time it takes to reach the prescribed intensity, maximum treatment intensity reached, subject treatment preference and discontinuations due to treatment discomfort between the two treatment protocols.

Once TMS therapy begins, adjustments to lower the stimulation intensity can begin immediately, as needed, for subject tolerance. The treater will assess if the subject can tolerate escalating the treatment MT by 10% at different time points. At each interval and the end of treatment, the treater will record the current %MT achieved. The goal will be to reach and sustain the target MT established by the treating physician of 120%MT. Once the target MT has been achieved and sustained for a certain period recording and increases of %MT may be discontinued but re-started at central intervals if %MT is subsequently reduced.

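### SAP 6.1.2 defines durations as start date minus end date, so every duration comes out zero or negative (minor; the primary VAS comparison is unaffected)

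*SAP*

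**What the plan says.** SAP 6.1.2 (Study Day) contains two date formulas. The first places an assessment relative to the first ramp day: "Study Day = Procedure/Assessment Date – Date of first day of the Dose Ramp Phase + 1". The section then turns to time in study, where "duration in study will be based on last study contact date which is the latest date of all follow-up visits" and other contacts such as adverse event dates and study exit. It closes with a general rule, introduced by "Duration variables will be calculated as follows": "Duration Days = Start Date – End Date".

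SAP 6.1 applies these principles wherever nothing else is specified. Neither document gives another formula for a duration.

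SAP 6.6.3 lists "the time it takes to reach the prescribed intensity" among the secondary endpoints, without a unit, a starting point or a formula. The underlying record is finer than a date. Protocol 13.1 says: "At each interval and the end of treatment, the treater will record the current %MT achieved". SAP 6.6.3 repeats this, Protocol 10.1 has the values entered in the CRF, and the worksheet in Protocol Attachment A and SAP Appendix C sets them out by 3:45 interval.

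**The concern.** An end date cannot fall before its start date, so the printed subtraction can never give a positive number. The two formulas in 6.1.2 therefore run in opposite directions. The dash in the duration rule cannot be read as meaning 'to', because the Study Day formula uses the same dash as a minus sign.

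The direct consequence is for duration in study, which the section itself introduces, and for any other date-based duration that is reported. One example is the duration of an adverse event, which Protocol 17.4 requires to be recorded. Besides having the wrong sign, the values rank in reverse: the longest duration becomes the smallest number.

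There is also a conditional consequence. Time to the prescribed intensity has no definition of its own, and an analyst who looks in the SAP for a duration formula finds this one. If it were used, the direction of the treatment comparison would reverse.

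**Working it through.** The documents state no numerical duration, so there is no figure to reproduce. The check applies the printed formulas to example dates.

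**Inputs**
- Duration rule: Start − End (SAP 6.1.2).
- Study Day rule: assessment date − first ramp day + 1 (SAP 6.1.2).
- Length of participation: "the study will consist of up to approximately 14 days" (SAP 4).
- Assumption: duration in study starts on the first ramp day. The SAP states the end of this period but not its start.

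**Step 1. One example.** First ramp day 1 March, last contact 12 March.
- Printed rule: 1 − 12 = −11.
- Study Day of last contact: 12 − 1 + 1 = 12.
- Terms swapped: 12 − 1 = 11.
- Terms swapped, plus 1: 12 − 1 + 1 = 12.

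**Step 2. Over the planned range.** Elapsed days run from 0 to 13, so the last row is a last contact on Study Day 14.

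| Days elapsed | Printed rule | Study Day | End − Start | End − Start + 1 |
|---|---|---|---|---|
| 0 | 0 | 1 | 0 | 1 |
| 1 | −1 | 2 | 1 | 2 |
| 4 | −4 | 5 | 4 | 5 |
| 8 | −8 | 9 | 8 | 9 |
| 13 | −13 | 14 | 13 | 14 |

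The printed rule falls as Study Day rises. Its absolute value equals the elapsed days in every row, so only the sign is wrong. The last two columns differ by a constant 1, which is a matter of convention.

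**Step 3. Time to the prescribed intensity, if it were taken from dates.** Under the escalation scheme in Protocol 10.1 (start at 90% MT, steps of 10% at 3:45 intervals), a subject who tolerates every step is at 90% from 0:00, 100% from 3:45, 110% from 7:30 and 120% from 11:15 of session 1.
- With the printed rule, later attainment gives a smaller number, so the slower group would appear faster. SAP 6.6.2.1 says that most inferential tests are one-sided. A one-sided p-value computed on the reversed values would become about 1 − p.
- With the sign corrected, everyone who reaches 120% in session 1 has the same value (0 days, or 1 with the added day). Reaching it in session 1 is the stated aim in Protocol 10.1, so such ties are to be expected.
- Non-treatment days count. A subject first treated on Friday who reaches 120% on Monday scores 3 days (4 with the added day) after 2 sessions.

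If the endpoint is counted in sessions, treatment minutes or 3:45 intervals, none of Step 3 applies.

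**Step 4. The primary analysis.** The candidate primary analyses in SAP 6.6.2 average the VAS scores taken at 3:45 and 18:45. No duration enters them.

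**The case against.** The strongest reply is that this is a typographical slip that corrects itself. The section ties duration in study to the last contact, a column of negative durations would be noticed at once, and the absolute values are right. No planned table, listing or test clearly depends on the formula: disposition (SAP 6.4) counts subjects, and safety (SAP 6.7) reports events, subjects and rates. All of this stands, and it makes the point minor. It does not make the rule correct. The formula is an operative instruction that nothing else in the documents corrects, and a silent correction by the programmer would be an undocumented departure from the plan.

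Three stronger readings are tempting, and the documents do not support them.

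- *The time-to-intensity comparison will be reversed.* SAP 6.6.3 does not link this endpoint to dates or to 6.1.2. The text that follows the list of secondary endpoints describes %MT recorded at intervals, which points to intervals or sessions. The same section allows secondary endpoints to be summarised descriptively only. The reversal, the session 1 ties and the weekend days are therefore conditional on a date-based calculation that the SAP does not specify.
- *The duration rule is the only elapsed-time rule in the SAP.* It is not. Study Day, a few lines above it, is correctly signed and could itself date the attainment of 120% MT.
- *Leaving out the +1 is a second error.* Study Day is a label that starts at 1, and an elapsed duration without the added day is a legitimate convention. What is missing is a statement of which convention is meant.

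**Conclusion.** Wrong as written, and minor. Applied literally, the rule returns zero or a negative number for every duration: −11 for 1 to 12 March, and −13 for a last contact on Study Day 14. The error is one of sign only. The Study Day convention gives 12 and 14 on the same dates, and a simple swap of terms gives 11 and 13.

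This conclusion needs only that end dates do not precede start dates. The two duration-in-study figures also assume that the period starts on the first ramp day.

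The primary VAS comparison is unaffected, and no stated conclusion of the trial is shown to be at risk. The related weakness in SAP 6.6.3 is that time to the prescribed intensity has no unit or starting point. That gap leaves room for a date-based calculation, which would be reversed under the printed rule and too coarse under the corrected one.

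**What to change.** 1. In SAP 6.1.2, replace the duration rule with: Duration Days = End Date − Start Date. State whether 1 is added. Adding it would match Study Day; leaving it out is equally acceptable. Name the start date for duration in study.
2. In SAP 6.6.3, state that time to the prescribed intensity is computed from the 3:45 interval log, in cumulative treatment minutes or completed intervals from the start of the first session, and not from calendar dates.

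The first change is one line plus a clause, and the second is a sentence. Both can go into an amended SAP before analysis, as SAP 7 provides. The interval log is already collected, so neither change needs new data, and neither alters how subjects are treated.

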### **6.1.3 Visit Windows**

Unless otherwise specified, visit based assessments will be analyzed for each analysis time point according to the nominal visit entered in the Case Report Form (CRF) regardless of whether it is out of window.

Statistical Analysis Plan		Page 9 of 18
Sponsor Neuronetics	Study Comfort Start	Version 1.0

#### **6.1.4 Statistical Significance**

Unless otherwise specified, hypothesis testing will be performed at the two-sided 0.05 significance level. P-values will be rounded to three decimal places. If a p-value is less than 0.001 it will be reported as “<0.001”. If a p-value is greater than 0.999, it will be reported as “>0.999”.

#### **6.1.5 Precision**

Unless otherwise specified, the following conventions will apply for data display. In general, percentages will be displayed to 1 decimal place. For continuous parameters, means, medians, and standard deviations will be reported to 1 additional decimal place than the measured value. Minimum and maximum values will be reported to the same precision as the measured value.

### **6.2 Analysis Populations**

*The following analysis populations are defined for analysis:*

1. **Intent-to-treat (ITT):** *The ITT population is defined as all subjects randomized.*
2. **Modified Intent-to-Treat (mITT):** *The mITT population is defined as all subjects in the ITT population where treatment was initiated.*
3. **Per protocol (PP):** *The PP population is defined as all subjects in with no significant protocol deviation, or adverse event that could compromise the validity of their assessments.*
4. **Safety (SAF):** *The SAF population is defined as all subjects that were exposed to any study device or treatment.*

The primary analysis set for efficacy endpoints and results will be the mITT set, with any other analysis sets defined as optional and supportive. The primary analysis set for safety endpoints and results will be the SAF set, with any other analysis sets defined as optional and supportive.

### **6.3 Handling of Missing Data**

All attempts will be made to limit the amount of missing data. Unless otherwise specified, no attempt will be made to impute missing data. If a data point is missing, that data point will not contribute to that portion of the analysis. The number of evaluable observations will be reported in analysis so that extent of missing data can be assessed.

In the case of partial adverse event onset date or date of death, the unknown portion of the date of the event will be imputed. If the month and year are known, the 15th of the month will be used for analysis. In the rare case that the date is fully unknown, the date will be imputed as the Date of first day of the Dose Ramp Phase. Imputation of partial dates is subject to the condition that it must occur on or after the informed consent date. In the case where the imputed date is prior to the informed consent date,

Statistical Analysis Plan		Page 10 of 18
Sponsor Neuronetics	Study Comfort Start	Version 1.0

the date of informed consent will be used. As death cannot occur before any documented subject contact, for date of death the imputed date of death must occur on or after last known contact in study.

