Since during the first few treatment sessions patients are typically ramped up to the desired treatment intensity (%MT) in a subjective manner by the treater, this process will be standardized during the study to minimize this confounding factor on perception of comfort. For all treatments, the first session will begin at 90% MT and the treater will ask the subject if they can tolerate the treatment intensity at 5 equal time intervals per treatment session (a treatment interval is 3 minutes and 45 seconds (3:45)). If tolerance is acceptable, the treater will increase the treatment intensity by 10% with the objective of reaching 120% by the end of the first treatment session. Dosage escalations during treatment will be limited to these 5 equal time intervals; however, dosage decreases can be done at any point due to patient intolerance. Treatment intensity changes will not be communicated to the subject. The treatment intensity achieved at each interval will be logged and documented in the study CRF. After the first interval (3:45), and after each stimulation session the subject will be asked to complete a "Comfort/Pain" VAS scale from (0-10cm). Once the subject completes the last 3:45 of a treatment session at 120%MT, they will begin their Crossover phase at the start of the next session. If a subject does not reach 120% MT by the end of the fifth treatment session, dose escalation attempts will continue, but they will transition to the Crossover phase. Refer to Attachment D for details of the Dose Escalation process.

Crossover Phase:

At the start of the 6th Treatment session or the session after the subject reaches the prescribed dose, the subject will be crossed over to the alternative treatment protocol and continue to alternate treatment each day for the next 3 treatments. Each day of these 4 treatment sessions,

at the first time interval (3:45) and the end of the session the subject will complete the comfort/pain questionnaire and be asked whether they preferred the current treatment, or the treatment received at the previous session (Todays Treatment, Last Treatment, No Difference).

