13 STUDY PROCEDURES

13.1 Study Visits

This is a prospective, randomized, single blind, cross-over study in an adult population. Only patients who have already consented to treatment with rTMS for MDD as diagnosed and prescribed by their treating physician will be enrolled in this study.

The study consists of up to 10 visits; Visit 1 for subject screening and Visits 2-10 for treatment administration which will be conducted concurrently with the subjects scheduled rTMS stimulation sessions. Study visits are estimated to take approximately 30 minutes in addition to the patient's regular rTMS treatment visits.

The study visits will be conducted in 2 phases:

Ramp Phase: The intent of the first 1-5 treatment visits is to evaluate the differences between treatment groups on subject comfort as the subjects are ramped to the prescribed treatment dose. This phase will also evaluate the impact of the two treatments on the ability and the time to achieve the prescribed treatment dose.

Crossover Phase: The intent of the crossover phase is to evaluate comfort differences and subject treatment preference between treatment groups and within subjects. In addition, the ability, and the time to reach the prescribed dose for those subjects who may not have reached it in the first 5 treatment sessions will continue to be assessed.

Details of the study visits are described below and on the subject flow diagram in section 14.2.

Screening/Baseline Study Visit

During Visit 1, the subject will be informed about the study and will be screened for eligibility to participate against the inclusion and exclusion criteria (including medication and medical

history). Eligible subjects will have the study and consent process explained to them and be provided the informed consent form to sign, or to return signed on Day 1 of TMS Treatment.

Ramp Phase:

Treatment Visit 1

Once signed consent is obtained, in addition to the treating clinicians' normal TMS instruction, subjects will receive instruction about the study procedures including the completion of comfort, preference and depression scales at the time of treatment for up to 9 treatments. Medication changes and recent medical history, including adverse events will be reviewed.

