If the subject reaches the prescribed %MT at any of these visits and sustains that MT through the final 3:45 minute time interval, the next study visit will be the start of the crossover phase of the study (Crossover Treatment 1). If the subject does not achieve the prescribed MT by the end of the 5th Treatment session, they will continue to Crossover Treatment 1 at the next visit, however, attempts to achieve the prescribed %MT should continue and be documented.

Crossover Phase

Visit 1

Subjects will be crossed over to the alternative treatment protocol, those who had received treatment X will then receive treatment Y and vice versa. Subjects will start treatment at the %MT established in the previous session and all study treatment assessments completed on Treatment Visits 2-5 of the Ramp Phase will be repeated and documented for each visit of the Crossover Phase.

Visits 2-4

Subjects will be crossed over to the alternative treatment protocol, those who had received treatment X will then receive treatment Y and vice versa. At the start of treatment, subjects will start treatment at the %MT established in the previous session and all study treatment assessments completed on Crossover visit 1 will be repeated.

Visit 4: Final Crossover Visit

At the start of treatment for Crossover visit 4, subjects will be crossed over to the alternative treatment protocol, subjects will start treatment at the %MT established in the previous treatment and all study treatment assessments completed on Crossover visit 1 will be repeated.

At the end of the final treatment, the treatment protocol for further TMS sessions will be determined by the clinician and the patient as part of their normal care. The treatment choice will be documented, and the subject will be exited from the study. See subject flow diagram in section 14.2 for additional information.

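### The SAP does not say how patients who never reach 120% MT enter the time-to-intensity outcome; read naturally, it compares reachers only

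*SAP*

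**What the plan says.** **The outcome.** SAP 6.6.3 lists among the secondary outcomes "the time it takes to reach the prescribed intensity, maximum treatment intensity reached". It allows superiority tests, non-inferiority tests or descriptive summaries, and gives no time origin, unit, event or censoring rule.

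**Non-reachers are foreseen.** Protocol 10.1: "If a subject does not reach 120% MT by the end of the fifth treatment session, dose escalation attempts will continue", while the patient moves on to the Crossover Phase. Protocol 13.1 says the same.

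**Which phase carries the comparison.** Protocol 13.1 says of the Ramp Phase: "This phase will also evaluate the impact of the two treatments on the ability and the time to achieve the prescribed treatment dose". Of the Crossover Phase it says that ability and time "for those subjects who may not have reached it in the first 5 treatment sessions will continue to be assessed".

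**What counts as reaching.** Several criteria govern visit flow or recording:
- Protocol 13.1, Treatment Visit 1: "If the subject reaches the prescribed %MT at Treatment Visit 1, the next study visit will be the start of the crossover phase", with no condition that the level be held.
- Footnote F of the schedule (Protocol 8, repeated in SAP Appendix A), and the recording rule in Protocol 13.1: held for 3:45.
- Protocol 13.1, Treatment Visits 2-5: the patient "sustains that MT through the final 3:45 minute time interval". Protocol 10.1 likewise uses the last interval.
- SAP 6.6.3, on recording: "achieved and sustained for a certain period recording and increases of %MT may be discontinued".

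**Analysis rules.** SAP 6.3 imputes nothing unless otherwise specified, and "If a data point is missing, that data point will not contribute to that portion of the analysis". SAP 6.1.1 summarises evaluable observations. Protocol 18.2 and SAP 6.6.2 name the t-test, Chi-square and Fisher's exact test as possible methods, and SAP 6.6.2 adds the Wilcoxon rank sum test. SAP 6.2 makes mITT the primary efficacy set.

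**The concern.** A patient who never reaches 120% MT has no observed time. With no rule for that patient, an analyst who applies the named tests and SAP 6.3 will most likely compare times among reachers. Whether a patient reaches target is itself a post-randomisation outcome, and the study hypothesis (synopsis) is that SoftStart changes it. If SoftStart works as hypothesised, more patients will be left out of the Dash group, and they will be the ones who tolerated treatment least. The remaining Dash patients then look quicker than the randomised group was, so a real difference can shrink, vanish or even change sign. A purely descriptive summary has the same weakness, because its means and medians also use only available values.

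There is a second, smaller gap. After the first switch the protocols alternate, so a patient who first reaches target in sessions 6-9 has received both. The SAP does not say how such a reach is credited.

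**Working it through.** The plan states no power, event rate or effect size for this outcome, so there is no figure to reproduce.

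**Step 1: do the visit criteria give the same event time?** Inputs: start at 90% MT, steps of 10%, intervals of 3:45, five per session (Protocol 10.1 and 14.2). From 90% to 120% takes (120 - 90)/10 = 3 steps. The earliest possible times are:
- target reached: 3 × 3:45 = 11:15
- held for 3:45: 4 × 3:45 = 15:00
- last interval completed: 5 × 3:45 = 18:45

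A patient at 120% from 11:15 to 15:00 who is then lowered has the event under the first two criteria and not under the third.

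**Step 2: how many patients would be left out?** Assume a constant chance p per session of reaching target. The chance of reaching it by session 5 is 1 - (1 - p)^5, and the expected number of non-reachers among 20 is 20(1 - p)^5.
- p = 0.20: reach 1 - 0.8^5 = 0.672; 6.6 of 20 left out.
- p = 0.45: reach 1 - 0.55^5 = 0.950; 1.0 of 20 left out.
- p = 0.50: reach 0.969; 0.6 left out.
- p = 0.70: reach 0.998; fewer than 0.1 left out.

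The mean time among reachers, Σk·p(1 - p)^(k-1) over k = 1 to 5 divided by the reach probability, is 2.56 sessions at p = 0.20 and 1.96 at p = 0.45, a gap of 0.60. The restricted mean over five sessions in all patients is [1 - (1 - p)^5]/p: 0.672/0.20 = 3.36 against 0.950/0.45 = 2.11, a gap of 1.25.

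**Step 3: power.** 20 per arm, two-sided 0.05 (SAP 6.1.4), time in sessions. Fisher is exact; the rest are simulated.

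| Assumed p, Dash vs SoftStart | t-test, reachers only | Fisher, ability to reach | Wilcoxon, non-reachers last | Log-rank, all |
|---|---|---|---|---|
| 0.20 vs 0.45 | 27% | 52% | 72% | 79% |
| 0.15 vs 0.35 | 16% | 55% | 68% | 74% |
| 0.25 vs 0.45 | 21% | 26% | 48% | 56% |
| 0.5 vs 0.7 | 28% | about 0% | 30% | 36% |
| 0.7 vs 0.85 | 21% | about 0% | 21% | 23% |

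With equal arms every method rejects in about 5% of trials or fewer, so the reachers-only test adds no false positives.

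**Step 4: can the direction change?** Assume reach of 95% on SoftStart and 60% on Dash.
- Same speed among reachers in both arms: the reachers' means are 2.23 and 2.23 sessions, although the restricted means over five sessions are 2.37 (SoftStart) and 3.34 (Dash).
- SoftStart's extra reachers are slow ones: the reachers' means are 2.62 (SoftStart) and 1.75 (Dash), which favours Dash, while the restricted means, 2.74 and 3.05, favour SoftStart.

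**Step 5: withdrawals.** At 0.20 vs 0.45, assume withdrawal for discomfort of 10% (Dash) and 2% (SoftStart) per session before target. Log-rank power is about 76% if these patients are censored on leaving and about 85% if they are kept as not reached through session 5.

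**The case against.** A reader might infer that the SAP excludes non-reachers by rule. It does not. SAP 6.3 concerns missing data points, a target never reached is a censored time, each patient's %MT is logged by interval, and mITT is the primary efficacy set. Where the SAP wants to restrict to patients who reached 120%, as in one option for the primary comfort analysis in 6.6.2, it says so. This objection stands: reachers-only is the natural reading, not a stated rule. It is natural because no named test takes a censored time, and no sentence ranks non-reachers last.

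A reader might also infer that a SoftStart benefit would go unseen. That is too strong. Ability to reach, maximum intensity and discontinuation for discomfort are separate secondary outcomes that keep these patients in part. At 0.20 vs 0.45 and 0.15 vs 0.35, either the reachers-only t-test or Fisher is significant in 66% and 61% of simulated trials (no multiplicity adjustment). That is below log-rank (79% and 74%) but far above the t-test alone.

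Nor is it right that the documents contain no event or comparison phase at all. SAP 1 says it is to be read with the protocol, so the Ramp Phase placement applies, and Appendix A repeats the 3:45 criterion. But these are visit-flow rules that differ from one another, and none is named as the endpoint event.

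Finally, Protocol 10.1 aims for 120% within the first session. If that is usually met, little is lost.

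**Conclusion.** The point holds as a gap in specification with a predictable consequence: non-reachers are foreseen, the time outcome has no rule for them, and the named methods lead naturally to a comparison conditioned on reaching target. Its size depends on reach rates that the documents do not give and on an assumed constant chance per session. If about a third of Dash patients miss target by session 5 (0.20 vs 0.45), the reachers-only test has 27% power against 72-79% for methods that keep everyone. If nearly all reach target early, the cost is 2 to 8 points. SAP 6.3 reports evaluable counts, so the exclusion would be visible but not corrected. The outcome is secondary, the study is declared exploratory and not based on formal power (Protocol 18.1, SAP 5), and this gap does not touch the primary comfort result. It is a cheap improvement.

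**What to change.** In SAP 6.6.3:
1. Name one endpoint event and one time unit, after the sponsor has reconciled the differing wording in footnote F (Protocol 8 and SAP Appendix A), Protocol 10.1, Protocol 13.1 (Visit 1 and Visits 2-5) and SAP 6.6.3 itself.
2. Compare the randomised first protocols in all mITT patients on Ramp Phase data, through session 5, and state that SAP 6.3 does not remove patients who did not reach target.
3. Use Kaplan-Meier and log-rank with non-reachers censored at the end of session 5, or a Wilcoxon test with non-reachers ranked last. Count withdrawal for discomfort as not reached through session 5, and censor other withdrawals when they leave. Protocol 13.2 already requires the reason to be recorded. The Wilcoxon alternative is clean only if no one leaves early for an unrelated reason.
4. Describe reaches after the first switch separately.

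The cost is SAP text, plus whatever protocol clarification the reconciliation needs; Protocol 19.7 requires an amendment if that change is significant. Protocol 13.1 lets recording of %MT stop once target has been held for 3:45, so that permission needs attention if the chosen event depends on the last interval. Reaches in sessions 6-9 leave the between-arm test.
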